## **10.2. Sample Size**

This is the first US-based study with topical ATI-50002 Topical Solution for the treatment of eyebrow loss due to AA, AU/AT. No formal power calculations will be performed.

# **11. TRAINING, MONITORING, DATA MANAGEMENT AND QUALITY ASSURANCE**

## **11.1. Training**

For each investigational center, there will be an initiation visit prior to enrolling any study subjects.

It is strongly recommended that all investigators, other evaluators, study nurses, study coordinators or other applicable personnel attend this visit. During this visit, participants will be trained to the protocol, study specific procedures, and the eCRFs. Those unable to attend the initiation visit must receive on-site training from an appropriately trained individual prior to participating in any of the procedures and evaluations in this study.

Clinical Research Associates (CRAs) and other applicable personnel will be trained prior to study initiation to familiarize CRAs with the disease, the Standard Operating Procedures (SOPs), the protocol and other study specific items. Team organization, communication and operational issues will also be discussed.

Aclaris Therapeutics, Inc. will provide an investigational center file to each center.

## **11.2. Monitoring**

The conduct of the study will be closely monitored by representatives of Aclaris Therapeutics, Inc. to verify adherence to ICH Good Clinical Practice (GCP) guidelines and applicable SOPs. Reports of these verifications will be archived with the study report. The investigator will allow the Aclaris Therapeutics, Inc. representatives designee and/or and any regulatory agency to have direct access to all study records, eCRFs, corresponding subject medical records, study medication dispensing records and study medication storage area, and any other documents considered source documentation. The investigator also agrees to assist the representative, if required.

### **11.3. Data Management**

Data management activities of this study will be subcontracted. Edit checks and review processes will be performed by the sub-contractor until all data clarifications are resolved. The data will be exported to be stored in SAS datasets (or equivalent) by the sub-contractor. After all data clarifications are resolved and subject's evaluability is determined, the database will be locked.

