### **6.6.3. Method of treatment assignment**

This study is an open-label study and all subjects will receive ATI-50002 Topical Solution 0.46%.

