## **6.9. Blinding**

### **6.9.1. Verification of blinding**

This study uses an open-label design.

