## **10. STATISTICAL ANALYSES**

### **10.1. Statistical Methods**

Summary descriptive statistics (N, mean, median, SD) by visit will be provided for all safety and efficacy parameters. Primary and secondary efficacy parameters are described below:

Mean change from baseline in eyebrow growth will be calculated as the mean change in the Clinician's Eyebrow Assessment (CEA) from Visit 2 (Baseline) compared to end of treatment (Visit 10). The CEA evaluates eyebrows on a scale from "No eyebrow hair" (grade 0) to "Full eyebrow hair" (grade 4).

Mean change from baseline in the Subject's Eyebrow Assessment (SEA) will be calculated from Visit 2 (Baseline) to end of treatment (Visit 10).

Mean change from baseline in the Subject's Eyebrow Satisfaction (SES) will be calculated from Visit 2 (Baseline) to end of treatment (Visit 10).

All efficacy summaries will be based on the per-protocol population including all subjects who have Baseline (Visit 2) and Visit 10 efficacy data and no major protocol violations.

Safety analyses will include descriptive statistics calculated on the safety parameters using the safety population. The proportion of subjects with treatment-emergent adverse events will be tabulated and presented by Medical Dictionary for Regulatory Activities (MedDRA) System Organ Class. Vital signs and clinically significant abnormal laboratory results will also be

CONFIDENTIAL  
Page 49 of 57

tabulated and presented. Change from baseline in the Local Tolerability Assessments (LTA) to end of treatment (Visit 10) will be summarized.

Data from all enrolled and treated subjects will be presented and summarized. Safety summaries will include listings by study medication of adverse events incidences within each MedDRA System Organ Class, and changes from pre-application values in vital signs. Adverse event summaries will be presented by study medication showing the proportion of subjects experiencing adverse events, both overall and by MedDRA System Organ Class.

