### **12.4. Study Conduct and Protocol Amendments**

With the exception of eliminating an immediate hazard to a subject, the investigator should not deviate from the protocol or implement any changes without prior written approval from Aclaris Therapeutics, Inc. and prior review and documented approval from the IRB/EC.

Changes that involve only logistical or administrative changes are allowed. The investigator should document and explain any deviation from the protocol. A protocol deviation is a non-adherence to protocol-specific study procedures or schedules that does not increase the risk to a study subject and does not affect the scientific integrity of the study.

A protocol violation is defined as any divergence from the protocol-specific study procedures or schedules that may result in an increased risk to a study subject or that affect the scientific integrity of the study. All protocol violations must be reviewed by the Medical Monitor and reported to the IRB by the Investigator, as directed by the IRB-specific procedures.

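### The only efficacy population rests on an undefined major-violation call that nothing keeps apart from known open-label outcomes, and no all-treated efficacy summary would show its effect

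*Combined protocol and SAP*

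**What the plan says.** Section 10.1, repeated in the synopsis under Statistical Methods, states: "All efficacy summaries will be based on the per-protocol population". Membership requires "Baseline (Visit 2) and Visit 10 efficacy data and no major protocol violations". Neither place gives an efficacy summary for all treated subjects, a sensitivity analysis or a rule for missing Visit 10 values. LOCF appears only in the abbreviation list.

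Section 12.4 supplies the only definition nearby: "A protocol violation is defined as any divergence from the protocol-specific study procedures or schedules", limited to divergences that may raise risk to a subject or that affect scientific integrity. It does not separate major from other violations. It adds: "All protocol violations must be reviewed by the Medical Monitor".

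On timing, Section 11.3 says that once data queries are closed and each subject's "evaluability is determined, the database will be locked". It does not say who determines evaluability, against what criteria, or with what data in view.

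On blinding, Section 6.9.1 says: "This study uses an open-label design". Under Section 6.6.3 all subjects receive the same active solution. Under Sections 6.3.3 and 7.1.1 the investigator or a designee scores the CEA. CEA, the Subject's Eyebrow Assessment (SEA) and photographs are all collected from Visit 5 (Week 4) onward.

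**The concern.** In a blinded trial, settling evaluability shortly before lock is safe because those deciding cannot link an exclusion to a treatment effect. In an open-label single-arm study the effect is each subject's own change from baseline, so the step protects only if the criteria are fixed in advance or the outcomes are withheld from the person applying them. The plan states neither safeguard.

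The judgement has room to move. Section 6.6.7 records compliance in the eCRF but gives no threshold for evaluability. Section 5.5.2 makes some topical products and cosmetic procedures near the eyebrow prohibited only if the investigator thinks they may affect safety or efficacy. If such an event were graded major more readily in a subject without regrowth, the reported mean change would be too high. There is no control arm and no second efficacy set against which to see it.

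A related route needs no judgement. A subject without Visit 10 data leaves every efficacy summary, whatever the reason, and Section 5.8 says that non-completers are not replaced.

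**Working it through.** The plan states no power, effect size or SD (Section 10.2), so there is no figure to reproduce. The check has two parts.

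**1. Can membership be settled before outcomes exist?**
- Section 10.1 makes Visit 10 efficacy data a condition of membership, so the set cannot be complete before the endpoint visit.
- By then an ungraded violation may have to be called major or not, while open-label scores from Visit 5 onward are on file.
- Section 11.2 gives sponsor representatives direct access to eCRFs and study records. This shows that access is possible, not that the person deciding uses it.

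**2. How far could the mean move?**

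Inputs: N = 12 (Section 5.1, approximate); CEA graded 0 to 4 (Section 7.1.1). Assumptions: one CEA change per subject, and all k excluded subjects have zero change.

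Excluding zero-change subjects leaves the sum of changes as it was, so the mean is multiplied by N/(N − k), whatever the number of responders:

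| k | Multiplier | Rise |
|---|---|---|
| 1 | 12/11 = 1.091 | 9% |
| 2 | 12/10 = 1.200 | 20% |
| 3 | 12/9 = 1.333 | 33% |

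Example on assumed data: 4 subjects gain 2 grades and 8 gain none, so the sum is 8.
- All treated: 8/12 = 0.67
- k = 1: 8/11 = 0.73
- k = 2: 8/10 = 0.80
- k = 3: 8/9 = 0.89

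The opposite direction, excluding one responder: 6/11 = 0.55, and 0.545/0.667 = 0.82, a fall of 18%.

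Sampling error in the same example: the sum of squares is 4 × (2 − 0.667)² + 8 × 0.667² = 10.67. SD = √(10.67/11) = 0.98 and SE = 0.98/√12 = 0.28. The shifts of 0.06, 0.13 and 0.22 grades are each below one SE.

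**Would a selective pattern be visible afterwards?** If exclusions were unrelated to outcome, the chance that all k fall on non-responders is C(8, k)/C(12, k) with 4 responders: 8/12 = 0.67, 28/66 = 0.42 and 56/220 = 0.25 for k = 1, 2, 3. With 3 responders, C(9, k)/C(12, k) gives 0.75, 0.55 and 0.38. An innocent process often produces the same pattern, so the data could not settle the question later.

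**Effect of the fix.** In the example, an all-treated Visit 10 mean that counts missing as no change stays at 8/12 = 0.67 whichever zero-change subjects are called non-evaluable.

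**The case against.** A reader might infer three stronger things, and the documents support none of them.

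- **That Section 11.3 is itself a faulty procedure.** Determining evaluability before lock is ordinary practice. What is missing is a list of criteria and a separation from outcomes.
- **That the decision is made by people who have seen the outcomes.** Section 11.3 names no one, does not place the evaluability decision after the closing of queries, and hands data management to a sub-contractor. It also does not mention the per-protocol set; that link is an inference, though a natural one.
- **That non-responders can be dropped for not responding.** Exclusion needs missing Visit 10 data or a major violation.

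There is also a contemporaneous trail. Compliance is documented at every post-baseline visit (6.6.7). More than 4 consecutive days without twice-daily application means removal (6.6.8). Use of a prohibited therapy is a listed example of a reason for discontinuation (5.6). All violations go to the Medical Monitor (12.4). This narrows the discretion, but none of it grades a violation as major.

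Section 10.1 also says that data from all enrolled and treated subjects will be presented. That could be read to include efficacy, but it sits in the safety text, names no efficacy measure, and cannot override an explicit rule for all efficacy summaries.

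Finally, the arithmetic is one-sided, exclusions unrelated to outcome carry no expected bias, and in a descriptive pilot no type I error is at stake. All of this stands, and it limits the size of the point. It does not supply the missing safeguard.

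**Conclusion.** The point holds as a gap in the plan. The single efficacy population depends on Visit 10 data and on an undefined major-violation call, nothing keeps the person making that call from knowing the outcomes, and no all-treated efficacy summary is planned. The documents show opportunity, not intent or occurrence.

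The rise of 9%, 20% or 33% for 1, 2 or 3 exclusions is an illustrative worst case. It assumes 12 subjects and zero change in everyone excluded. It is not a forecast, and in the worked example each shift is smaller than one standard error. The harm would be an inflated descriptive mean. That still matters, because Section 3.2 gives demonstrating efficacy as part of the study's purpose and there is no control arm to put the mean in context.

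**What to change.** 1. **Section 10.1 and synopsis.** Present every efficacy summary for all treated subjects beside the per-protocol one, with a stated rule for missing Visit 10 values. One option is observed data by visit plus a Visit 10 summary counting missing as no change from baseline. For an eyebrow at CEA grade 0 at baseline, no change is the lowest possible result, so that rule cannot flatter the CEA mean.
2. **Section 10.1 or 12.4.** List the major violations, and fix the list before the first post-baseline efficacy assessment, the first subject's Visit 5. Waiting until the first Visit 10 would be too late, because open-label CEA, SEA and photographs accrue from Week 4.
3. **Section 11.3.** State that evaluability is classified against that list from a deviation and compliance listing that omits post-baseline CEA, SEA and Subject's Eyebrow Satisfaction (SES) scores and photographs.

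This is a cheap improvement: a second column in each efficacy table and one extra listing, with no change to treatment or visits. The downside for the sponsor is a possibly less favourable mean.

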### **11.4. Quality Assurance**

The study is conducted under the sponsorship of Aclaris Therapeutics, Inc. in compliance with the applicable regulatory requirements as well as applicable ICH guidelines, Declaration of Helsinki, and in respect of the Aclaris Therapeutics, Inc. and/or sub-contractor SOPs for study conduct and monitoring.

Audits may be carried out by Aclaris Therapeutics, Inc. or Aclaris Therapeutics, Inc.'s representatives and inspections may be performed by regulatory authorities or IRB/ECs before, during or after the study. The investigator will provide the auditing/inspecting group direct access to all study records (e.g., eCRFs, subject medical records, study medication dispensing records) and the investigational center study facilities. The investigator and study staff will be available and will assist the auditing/inspecting groups as appropriate.

## **12. ETHICS AND GENERAL STUDY CONDUCT CONSIDERATIONS**

### **12.1. Institutional Review Board (IRB)/Ethics Committee (EC)**

This protocol, informed consent form, any information provided to subjects, subject-recruiting advertisements, and any amendments to these items will receive IRB/EC approval prior to use.

The IRB/EC must receive a copy of the Investigator's Brochure, all protocol amendments, safety reports and other study related information as required by regulation or the IRB/EC procedures.

### **12.2. Ethical Conduct of the Study**

The rights, safety and well-being of the subjects are the most important considerations in this study and take priority over the interests of society and science.

This study will be conducted in accordance with the ethical principles originating from the Declaration of Helsinki, the ICH E6 GCP guideline, local regulatory requirements and, at US investigational sites, in compliance with HIPAA. The study will be conducted in compliance with the IRB/EC approved version of the protocol and any applicable amendments.

This protocol, informed consent form, any information provided to subjects, subject-recruiting advertisements, and any amendments to these items will receive IRB/EC approval prior to use. Subjects will provide voluntary informed consent prior to initiation of any study related procedures.

CONFIDENTIAL  
Page 51 of 57

### **12.3. Subject Information and Consent**

All subjects who participate in this study must be fully informed about the study in accordance with the GCPs, federal regulations, local regulations and, at US investigational sites, with HIPAA. The ICF will contain all the required elements in compliance with the current ICH E6 GCP guideline, local regulatory requirements. The investigator must have a defined process for obtaining voluntary informed consent from every subject.

The ICF, approved by an IRB/EC, will be fully explained to the subject. Prior to any study related procedures, including washout from therapies, the subject will voluntarily sign and date the ICF. The investigator must maintain each subject's ICF in the investigational center's study file and must provide each subject with a copy of the signed and dated ICF.

### **12.4. Study Conduct and Protocol Amendments**

With the exception of eliminating an immediate hazard to a subject, the investigator should not deviate from the protocol or implement any changes without prior written approval from Aclaris Therapeutics, Inc. and prior review and documented approval from the IRB/EC.

Changes that involve only logistical or administrative changes are allowed. The investigator should document and explain any deviation from the protocol. A protocol deviation is a non-adherence to protocol-specific study procedures or schedules that does not increase the risk to a study subject and does not affect the scientific integrity of the study.

A protocol violation is defined as any divergence from the protocol-specific study procedures or schedules that may result in an increased risk to a study subject or that affect the scientific integrity of the study. All protocol violations must be reviewed by the Medical Monitor and reported to the IRB by the Investigator, as directed by the IRB-specific procedures.

### **12.5. Regulatory Documents**

The investigator must maintain a study file containing current and complete regulatory documentation in compliance with the current ICH E6 GCP guideline. This file will be reviewed as part of the routine monitoring for this study.

### **12.6. Contractual Requirements**

A contractual agreement will be signed between Aclaris Therapeutics, Inc. and each investigator. This document will contain supplemental information, including financial terms, confidentiality, study schedule, third party responsibility, and publication rights.

## **12.7. Data Collection and Archiving**

### **12.7.1. Data collection**

The Investigator must maintain required records for all study subjects. Data for this study will be recorded in the subject's source document and on the eCRFs. All data on these eCRFs should be recorded completely and promptly. A copy of the completed eCRFs for each subject will be retained by the investigational center.

Records of the subject's participation in this study will be held confidential except as disclosure is required by law. The study doctor, the sponsor, persons working on behalf of the sponsor, and under certain circumstances, the United States Food and Drug Administration and the Institutional Review Board will be able to inspect and copy confidential study-related records that identify subjects by name. Therefore, absolute subject confidentiality cannot be guaranteed. If the results of this study are published or presented at meetings, the subject's identity will not be revealed.

### **12.7.2. Source documentation**

Investigators must keep accurate separate records (other than the eCRFs) of all subjects' visits that include all pertinent study related information. A statement should be made indicating that the subjects have been enrolled in this clinical study and have provided written informed consent. Any AEs must be completely documented. Source documentation includes results of any diagnostic tests conducted during the study.

### **12.7.3. Archiving**

All pertinent data, samples, photographs, correspondence, original or amended protocol, reports and all other material relating to the study will be maintained securely in Aclaris Therapeutics, Inc. /contract research organization/investigator archives for the legally required duration for archiving.

The investigator should maintain the essential study documents as specified in ICH GCP, and in compliance with all regulatory requirements. The investigator should ensure these documents are protected from accidental destruction or disposal.

If the Investigator needs to re-assign responsibility for maintaining these documents (e.g., due to retirement) it must be transferred to a person willing to accept this responsibility. The investigator must notify Aclaris Therapeutics, Inc., in writing, of the name and address of the new individual.

